## Study Endpoints and Hypotheses to Test

### Study Endpoints

Primary outcomes include all-cause mortality, acute myocardial infarction (AMI), and late coronary revascularization (PCI or CABG beyond 60 days after CMR).

Secondary outcomes include non-fatal cardiac events (including cardiac hospitalizations for unstable angina or heart failure, heart transplant, significant ventricular arrhythmias, and strokes), alteration of diagnostic and therapeutic decision, and cardiac event-weighted QALY.

The specific aims of this project are listed below:

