### **Specific Aim 2 – Assessment of the impact of CMR-guided invasive coronary revascularization, compared with medical therapy, on primary outcomes**

Sub-aim 2.1 Using a propensity score-matching analysis, test the hypothesis that in real-world clinical practice that stress CMR perfusion imaging-guided use of invasive coronary revascularization (INT) (defined by INT performed within 60 days after CMR) offers *AMI-free, coronary revascularization-free, survival benefits* over medical therapy (MED) in patients with suspected ischemia. We will estimate the # lives saved per 100 patients treated with INT versus MED (based on predicted primary outcome rate amongst MED)–(predicted primary outcome rate amongst INT)

Sub-aim 2.2 Using a propensity score-matching analysis, test the hypothesis that in real-world clinical practice that stress CMR perfusion imaging-guided use of INT offers *survival benefits free of primary or secondary outcomes* over MED in patients with suspected ischemia.

Sub-aim 2.3 The preferred initial treatment for patients with stable ischemic heart disease (SIHD) is the best available medical therapy. The benefits of using physiologic ischemia-based guidance to performing INT has been shown in the FAME and FAME-2 trials where fraction-flow-reserve was used to assess physiological significance of coronary stenosis. In FAME (multi-vessel SIHD) and FAME 2 (single or multi-vessel SIHD) trials: a 29% and 66% relative risk reduction of primary outcome at 2-years were reported, respectively. CMR perfusion assessment had demonstrated remarkable correlation to FFR based assessment of coronary physiologic significance. For sub-aim 2.3, test the hypothesis that comparing to the FAME-2 primary outcome rate of patients managed by medical management alone, CMR-guided INT patients have a relative risk reduction of 2-year primary outcomes  $\geq 30\%$ .

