#### **c) Clinical Outcomes within 4 years after CMR**

Primary outcomes: a) All-cause including cardiac mortality, b) new acute MI, within 4 years after CMR imaging, and c) late coronary revascularization (PCI or CABG beyond 60 days after CMR);

Secondary outcomes: heart failure hospitalization, unstable angina hospitalization, heart transplantation, significant ventricular arrhythmias, and strokes, within 4 years after CMR. Times to all of the above events will be collected. Other supportive data: angiographic reports including PCI details, CABG operative reports. Repeat events of all non-fatal outcomes will be collected using our web-based data structures (Appendix A4).

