## Sample Size

### For sub-aim 1:

The rate of cardiac hard events (death and acute MI) is estimated based on reported evidence of 0.5% and 6% per year for patients who have absence and presence of ischemia on CMR perfusion imaging, respectively. We plan to collect follow-up events for a 4-year period after CMR. Based on prior evidence, prevalence of ischemia on CMR perfusion was 23% in referred patients.

With a sample size of 2,200 patients, 506 (23%) are assumed to be with presence of ischemia and 1694 (77%) with absence of ischemia. With incidences of 6% and 0.5% per year and a 4-year follow-up, a total of 124 of 506 patients with ischemia and 36 of 1694 patients with no ischemia are expected to experience an event, i.e. a total of 150 patients with event.

A sample size of 2,200 patients overall and 150 patients with event in a 4-year follow-up is regarded sufficient to run multivariable analysis with up to 10 variables.

With regards to the sample size considerations on the time-to-event analysis, the following settings and assumptions were used:

- Power = 80%
- Level of significance (two-sided) = 5%
- Assumed proportion in control group (i.e. no revascularization) = 77%
- Total sample size = 2,200 patients
- Number of events = 150 in total sample
- 4-year follow-up for all patients available
- The hazard ratio is estimated by a Cox proportional hazard model

With a sample size of 2,200 patients and an event rate of 124 in group 1 and 36 in group 2, a hazard ratio of 0.59 can be detected with the above mentioned settings and assumptions (i.e. 41% risk reduction rate).

For sub-aim 2.3 (comparison to the historical FAME 2 study

As reported in published data (own BWH dataset and [name] et al Circulation 2011 Apr 12;123(14):1509-18), the event rate of patients who underwent revascularization guided by CMR ischemia (i.e. CMR physiologic guidance) is about 5% per year, i.e. 10% in a 2-year follow-up. In the

historic fame-2 study, the 2-year event rate of patients who did not use physiological guidance (N=441), was 19.5%. With a power of 80%, a two-sided alpha of 5% and an assumed difference under H1 of -9.5%, the sample size of patients in this registry needs to be at least 180 patients.

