**Step 1: Propensity Score to Treatment** We plan to structure the study analysis of observational data in SA1 to mimic a randomized clinical trial: a) assignment of coronary intervention (INT) vs. medical therapy (MED) is based on the therapy selected in the initial 60 days after imaging and b) nonrandomized treatment adjusted for via a propensity score. Either PCI or CABG will define coronary revascularization. Follow-up time begins at the time of the index stress CMR imaging. To adjust for non-randomization of treatment, a single propensity score will be developed using logistic regression to model the decision to refer to revascularization considering all factors known to influence the referral decision. This single composite propensity score represents the probability of treatment assignment, which will be included in all subsequent survival models (step 2) associating stress CMR perfusion guided-treatment with the respective endpoints in each of the 3 sub-aims. This adjustment reduces the bias introduced by nonrandomized referral to INT in practice. While all factors known to influence this referral decision will be considered for entry into this logistic regression model, based on existing literature, the most likely predictors of referral to INT include % ischemic myocardium (% myocardial mass based on number of segments, by CMR), typical angina symptoms (yes if positive response to 2 of 3 Diamond and Forrester qualities, else no), infarct size (LGE size, grams of myocardial mass), ischemic ST changes on rest ECG (yes/no), pre-test coronary disease probability (ordinal), and prior cardiac catheterization (yes/no). We anticipate that 10-15% of patients (~n=300) received INT so model over-fitting will not occur when constructing this logistic regression model.

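### Sub-aim 2.3 sets a registry outcome that omits revascularization in the first 60 days after CMR against FAME-2's own primary outcome rate, with no step to align the two, so part of any difference, in either direction, can come from the endpoint definition

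*Combined protocol and SAP*

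**What the plan says.** **Registry outcome.** Study Endpoints defines the primary outcome as all-cause death, acute MI and "late coronary revascularization (PCI or CABG beyond 60 days after CMR"). Data to Collect, part c, repeats the same restriction. Death and MI carry no such window.

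**Registry group.** Sub-aim 2.1 introduces the invasive group (INT) as "defined by INT performed within 60 days after CMR". Step 1 of the aim 2 analysis adds: "Follow-up time begins at the time of the index stress CMR imaging". The period that assigns a patient to INT is therefore also the period in which no revascularization is an event.

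**Benchmark.** Sub-aim 2.3 is worded as "comparing to the FAME-2 primary outcome rate of patients managed by medical management alone, CMR-guided INT patients have a relative risk reduction of 2-year primary" events, with a threshold of 30% or more. The Sample Size section gives the figure: "the 2-year event rate of patients who did not use physiological guidance (N=441), was 19.5" per cent. The same section puts the registry side at a rate that "is about 5% per year, i.e. 10% in a 2-year follow-up", without saying which events make up that rate.

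**Alignment.** The aim 2 analysis heading and Step 2 cover sub-aims 2.1 and 2.2. No rescoring, common landmark or sensitivity analysis is described for 2.3. The two descriptions of the FAME-2 group (medical management alone in Specific Aim 2, no physiological guidance in Sample Size) also differ and should be reconciled.

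**The concern.** Sub-aim 2.3 rests on the gap between two single rates from two sources. An event that one definition counts and the other does not goes straight into that gap. Propensity adjustment within the registry cannot remove it, and it would remain if the two populations had identical case mix.

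The protocol describes FAME-2 as guided by fractional flow reserve, so its outcome cannot be defined by a window after a CMR. On the registry side, a repeat PCI or CABG before day 60 in an INT patient is never a primary event. What is at stake is how far the headline claim of a 30% or greater relative reduction can be attributed to CMR-guided revascularization.

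**Working it through.** **1. The plan's own figure.** Inputs from Sample Size: registry rate 10%, benchmark 19.5%, N=441, two-sided 5%, power 80%. I used a two-sample z-test with pooled variance under the null and N=441 fixed. At n=180:

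- Pooled rate = (180×0.10 + 441×0.195)/621 = 0.1675
- SE0 = √[0.1675×0.8325×(1/180 + 1/441)] = 0.03303
- SE1 = √(0.10×0.90/180 + 0.195×0.805/441) = 0.02926
- Power = Φ[(0.095 − 1.96×0.03303)/0.02926] = Φ(1.03) = 85.0%

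The smallest n with 80% power is 154, or 172 with a continuity correction. The stated minimum of 180 is not reproduced exactly but is conservative for this test. The point does not depend on it.

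**2. The two endpoints side by side.**

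| | Registry | FAME-2 benchmark |
|---|---|---|
| Components | Death, MI, late PCI/CABG | Not stated |
| Time zero | Index CMR | Not stated |
| Revascularization, first 60 days | Not an event | Not stated |
| Revascularization, later | Any PCI or CABG | Not stated |

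Row 3 can only lower the registry count. Row 4 could raise it relative to the benchmark if the FAME-2 rule is narrower.

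**3. Distance to the 30% threshold.** The planned reduction is 1 − 10/19.5 = 48.7%. A 30% reduction corresponds to 0.70×19.5 = 13.65%. Definition alone would have to account for 19.5 − 13.65 = 5.85 points.

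**4. Sensitivity, favourable direction.** Assumption: x points of the 19.5% are events that the registry definition would not count, and INT has no true benefit. The registry then shows p = 0.195 − x/100. The documents do not give x, so a range is shown.

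- Chance of a significant result in favour of INT = Φ[(0.195 − p − 1.96×SE0)/SE1]
- n=300 (the INT number anticipated in Step 1), x=1: Φ[(0.010 − 1.96×0.02942)/0.02930] = Φ(−1.63) = 5.2%
- n=300, x=2: Φ[(0.020 − 1.96×0.02917)/0.02893] = Φ(−1.28) = 9.9%
- Chance that the point estimate reaches a 30% reduction = Φ[(0.1365 − p)/√(p(1−p)/n + 0.49×0.195×0.805/441)]

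| x (points) | Apparent reduction, x/19.5 | False positive, n=300 | False positive, n=180 | Estimate reaches 30%, n=300 |
|---|---|---|---|---|
| 0 | 0% | 2.5% | 2.5% | 1.3% |
| 1 | 5.1% | 5.2% | 4.6% | 3.1% |
| 2 | 10.3% | 9.9% | 8.0% | 6.6% |
| 3 | 15.4% | 17.5% | 13.1% | 12.9% |
| 4 | 20.5% | 28.2% | 20.5% | 22.7% |

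If INT really is at 10% and the matched benchmark is 19.5 − x, power at n=180 falls from 85% to 77% (x=1), 67% (x=2) and 55% (x=3).

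**5. Sensitivity, opposite direction.** Assumption: the registry counts x points of later procedures that the benchmark does not.

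- With no true benefit and n=300, the first formula in step 4 with p = 0.205 and 0.215 gives 1.1% and 0.5%, below the nominal 2.5%.
- With a matched registry rate of 10%, the observed rate is 11% or 12%. The reduction shrinks from 48.7% to 1 − 11/19.5 = 43.6% or 1 − 12/19.5 = 38.5%, and power at n=180 falls to 75% or 62%.

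**The case against.** The strongest reply is that the 60-day window has a stated purpose. The aim 2 analysis section explains that revascularization within 60 days followed from the imaging result, whereas later referral tended to reflect worsening clinical status. The window defines treatment assignment, and excluding the index procedure is unavoidable. Deaths and MIs inside it still count. This stands as a defence of the rule within the registry, where INT and medical patients share one definition. It does not carry over to an external rate scored under another definition.

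A second reply is that the mismatch has no documented size. This is correct, and the figures above are conditional on an assumed x.

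A reader might infer that the mismatch favours INT. The documents do not support that as a net statement, because the registry counts every PCI or CABG after day 60 with no limit on urgency or indication, and this could pull the other way.

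A reader might also infer that a mismatch of 1 or 2 points is enough to produce the 30% claim. It is not. It roughly doubles to quadruples the false-positive rate of a test of any difference, which is the test that the sample size uses. The chance that the point estimate reaches 30% is only 3.1% to 6.6% at n=300.

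Finally, simply removing the 60-day exclusion could score planned staged procedures as INT failures. That objection is sound and shapes the fix.

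**Conclusion.** The point holds as a comparability problem: carried out as written, sub-aim 2.3 compares two 2-year rates that are not shown to count the same events. A reader might go further and conclude that the 19.5% does contain early revascularization that the registry omits. The documents show only that the FAME-2 outcome is not anchored to a CMR; its components, time zero and rule for repeat procedures are absent.

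Direction and size are therefore both open. The quantified range assumes no true benefit, independent binomial rates, the plan's N=441, and a mismatch acting wholly in one direction. Under those assumptions a small favourable mismatch matters for a simple difference test, but a 30% reduction from definition alone would require 5.85/19.5 = 30% of all benchmark events to fall outside the registry definition. The problem is confined to sub-aim 2.3. It should be corrected before analysis, but it does not affect Aim 1 or sub-aims 2.1 and 2.2.

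**What to change.** For sub-aim 2.3 only:

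1. State the FAME-2 primary-outcome definition and its time zero beside the 19.5% in Sample Size.
2. Base the main comparison on an endpoint that can be scored identically in both sources. Use the FAME-2 definition where the collected event dates and PCI/CABG reports allow it, treating planned staged procedures as that definition does. Otherwise use death plus MI against the FAME-2 rate for those components.
3. Restate the 10%, the 19.5% and the minimum of 180 patients on that endpoint.
4. Report the present unmatched comparison as a sensitivity analysis.

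**Cost.** One derived endpoint for about 220 to 330 INT patients (10% to 15% of 2,200), plus changes to Specific Aim 2 and Sample Size. Whether existing data suffice must be checked: the outcome form in Appendix A4 shows procedure dates and a description field, but no field for urgency or for planned versus unplanned. The death-plus-MI fallback needs a FAME-2 component rate that the documents do not give. Sub-aim 2.3 would also use a different endpoint from 2.1, and with a narrower endpoint the expected reduction and the power may be less favourable.

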### **Specific Aim 3 – Cost-effectiveness analysis**

Using a propensity score-matching analysis, test the hypothesis that in real-world clinical practice that stress CMR perfusion imaging-guided use of INT offers *cost-effectiveness benefits* over MED in patients with suspected ischemia.

### **Database Infrastructure of Database and DICOM Storage**

A HTTP secure web database focusing on collecting clinical data in CMR (CMR Cooperative) (<https://cmrcoop.partners.org/>) has been established and collecting CMR data since 2008. There are currently 45 US centers using this web-based HIPAA compatible database which allows complete de-identification of all patient information, multicenter research, and DICOM anonymized linkage and storage. In addition, this web-tool was designed to facilitate detailed but simple-to-use interface in collecting all data (below) relevant to this multicenter study. Several pages of this web-tool are displayed in the Appendix Section.

### **Data to Collect**

#### **a) Patient Demographics**

Basic patient demographic data including age, gender, cardiac and non-cardiac medical history, and medications in use at the time of imaging. Detailed collection of cardiac symptoms and reasons for imaging referral including the Diamond and Forrester symptom scores, New York Heart Association Grade, pre-test CAD risk scores will be determined. Key demographic variables (amongst others) are shown in Appendix A2.

#### **b) CMR Imaging**

Detailed contrast uses including types, brands, dosages, and methodology of contrast injections will be collected. Retrospective review of site-reported extent of myocardial ischemia by CMR, based on a 17-segment AHA nomenclature, as "mild" (<=3 segments), "moderate" (4-7 segments), or "severe" (>=8 segments). CMR based LVEF, infarct location and number of segments with LGE. Please refer to Appendix A3 for subset of the examples of the web-based data collection.

#### **c) Clinical Outcomes within 4 years after CMR**

Primary outcomes: a) All-cause including cardiac mortality, b) new acute MI, within 4 years after CMR imaging, and c) late coronary revascularization (PCI or CABG beyond 60 days after CMR);

Secondary outcomes: heart failure hospitalization, unstable angina hospitalization, heart transplantation, significant ventricular arrhythmias, and strokes, within 4 years after CMR. Times to all of the above events will be collected. Other supportive data: angiographic reports including PCI details, CABG operative reports. Repeat events of all non-fatal outcomes will be collected using our web-based data structures (Appendix A4).

#### **d) Costs**

Please see the attached word file figure 3 and the excel file budget (GCMR stress perfusion budget).

All costs of imaging tests, medical care, and cardiac procedures will be based on regional national average inflated to the year of study analysis.

Imaging: Initial and downstream performance of any imaging studies (stress CMR, stress nuclear imaging including SPECT or PET, coronary CTA, stress echocardiography, and stress treadmill exercise test without imaging).

Medical care: any treatment of acute MI, heart failure or unstable angina admissions, and heart transplantation.

Cardiac procedures: coronary angiography with and without intervention, CABG, ICD and pacemaker implantation.

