### Rationale and the Expected Deliverables of this Project

This proposal (Project 1) aims to assess the clinical impact of stress CMR perfusion guided treatments on patient outcomes in a 2,200 consecutive multicenter patient cohort, referred for assessment of myocardial ischemia in the United States. In the 3 specific aims presented below, we aim to obtain real-world evidence in patient outcomes including mortality and non-fatal cardiac outcomes, downstream cardiac procedures, invasive and non-invasive testing, costs in health care dollars based on national averages, and cardiac event-weighted quality adjusted life years (QALY). We believe these specific aims will provide the core evidence that medical insurance agencies and industries most sought after in making their reimbursement and payment decisions in the United States, towards the use of stress CMR perfusion imaging in patients with chest pain syndromes. At the end of the funding period, we expect multiple publications to result from each of the 3 specific aims which represent these core evidence.

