#### **e) Effectiveness**

Quality-adjusted life years (QALY) over a 4-year period calculated by validated utility-weighting ([www.cearegistry.com](http://www.cearegistry.com)).

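### The cost list has no line for stroke or ventricular arrhythmia, two of the five non-fatal secondary events, although both probably enter the QALYs

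*Combined protocol and SAP*

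**What the plan says.** Section d) Costs sets out what will be priced. Besides imaging tests there are two lines. The first is "Medical care: any treatment of acute MI, heart failure or unstable angina admissions, and heart transplantation". The second is "Cardiac procedures: coronary angiography with and without intervention, CABG, ICD and pacemaker implantation". Neither line is worded as a set of examples. The section also points to material outside the protocol: "Please see the attached word file figure 3 and the excel file budget (GCMR stress perfusion budget".

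Study Endpoints defines the secondary outcomes as "non-fatal cardiac events (including cardiac hospitalizations for unstable angina or heart failure, heart transplant, significant ventricular arrhythmias, and strokes", and the same sentence goes on to name the event-weighted QALY. Section c) Clinical Outcomes repeats the five events: "Secondary outcomes: heart failure hospitalization, unstable angina hospitalization, heart transplantation, significant ventricular arrhythmias, and strokes, within 4 years after CMR". It adds that event times and repeat events will be collected.

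On the effect side, the Rationale section speaks of "cardiac event-weighted quality adjusted life years (QALY". Section e) Effectiveness gives the method: "Quality-adjusted life years (QALY) over a 4-year period calculated by validated utility-weighting". No section lists which events receive a weight.

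The outcome form in Appendix A4 has dated fields for stroke, VT/VF or ICD therapy, ICD-shock hospitalization, LV assist device and cardiac resynchronization therapy.

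**The concern.** A cost-effectiveness ratio is interpretable only if an event that reduces health also brings its expense into the numerator. Here the cost list follows the secondary endpoint list closely, except that two events are missing and no reason is given. If stroke and ventricular arrhythmia reduce QALYs but carry no price, a strategy that produces more of them is charged the health loss and excused the treatment cost.

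Aim 3 is where this matters. Its stated hypothesis compares revascularization with medical therapy. Its analysis section compares five diagnostic strategies and cites $20,429 per QALY for a strategy based on coronary CTA alone. The Rationale section says the evidence is meant for insurers' reimbursement decisions. An event set that differs between the two halves of the ratio is a weakness such readers would look for.

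**Working it through.** The plan gives no ICER, unit prices, utilities, or stroke or arrhythmia rates for this cohort, so there is no figure to reproduce. The check is an item-by-item comparison of the endpoint sections, Appendix A4 and d) Costs.

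| Event or procedure | Where it is counted or collected | Line in d) Costs? |
|---|---|---|
| Acute MI | Primary outcome | Yes |
| Late PCI or CABG | Primary outcome | Yes |
| Heart failure admission | Secondary outcome | Yes |
| Unstable angina admission | Secondary outcome | Yes |
| Heart transplant | Secondary outcome | Yes |
| Significant ventricular arrhythmia | Secondary outcome | No |
| Stroke | Secondary outcome | No |
| ICD or pacemaker implantation | A4 form | Yes |
| ICD-shock hospitalization | A4 form only | No |
| LV assist device | A4 form only | No |
| Cardiac resynchronization therapy | A4 form only | Not named; may fall under ICD and pacemaker implantation |

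**Result.** 3 of the 5 non-fatal secondary events are costed and 2 are not.

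**The QALY side.** Study Endpoints classes stroke and ventricular arrhythmia as non-fatal cardiac events, and the QALY is weighted by cardiac events. The natural reading is that both carry a weight. Section e) Effectiveness does not confirm it.

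**How an omission acts on the ratio.** For strategies 1 and 2,

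ICER = (C1 − C2) / (E1 − E2).

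Suppose an event has probability p1 and p2 per patient under the two strategies and unit cost c. If it is left out of the cost list, the numerator lacks (p1 − p2) × c. If its utility loss is kept, the ICER is in error by

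(p1 − p2) × c / (E1 − E2).

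Two things follow. If the event is equally frequent under both strategies, the error is zero. If it is not, the strategy with more events looks too cheap. The documents give none of p1 − p2, c or E1 − E2, so neither the size nor the direction can be calculated.

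**The case against.** Several arguments on the other side have force.

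**The list of weighted events is never given.** In Study Endpoints the wording runs "heart transplant, significant ventricular arrhythmias, and strokes), alteration of diagnostic and therapeutic decision, and cardiac event-weighted QALY". The bracket closes before the QALY appears, so the bracketed events are not formally its definition. This stands: the mismatch is an inference, though a strong one for stroke and ventricular arrhythmia. If both were left out of the QALY as well, two counted outcomes would drop out of the economic analysis, and the plan should say so.

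**The cost specification is partly unseen.** The Word figure and Excel file may price more events. This also stands as a condition on the finding. The Aim 3 analysis section says the model will draw on all cost and outcome data from the study, but that does not add a cost line; d) Costs defines what the cost data are.

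**ICD implantation already covers arrhythmia.** It covers the device, not an admission for VT/VF or for shocks.

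**Comparability with the published benchmark.** Which events the published CTA model costs cannot be seen here, so a longer list need not bring this study closer to it. That is a reason to report the list, not to leave counted events unpriced.

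A reader might also draw two stronger conclusions that the documents do not support.

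- *That the mismatch extends to ICD-shock admission, LVAD and CRT.* These appear only on the A4 form and are not named endpoints. Nothing gives them a utility weight, and CRT may already be costed under the device line.
- *That the distortion can be put in dollars.* Assume 0.5–1.0% strokes per year. Then 2,200 × 4 × 0.005 = 44 to 2,200 × 4 × 0.01 = 88 strokes. Assume also $20,000–60,000 per stroke, a difference of 1 stroke per 100 patients between strategies, and a gain of 0.02–0.05 QALY. The ICER then moves by $200/0.05 = $4,000 to $600/0.02 = $30,000. All four inputs are assumptions. A difference of 1 per 100 is 25–50% of the assumed 4-year risk of 2–4%. Suppose the excess came only from early revascularization, which the Specific aim 2 section expects in 10–15% of patients, against a comparator with none. It would then need 0.01/0.15 = 6.7% to 0.01/0.10 = 10% extra strokes among those revascularized. The range shows that the ratio can be sensitive to the omission; it is not an estimate of the error.

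**Conclusion.** The point holds in a limited form. As written, d) Costs prices three of the five non-fatal secondary events and omits stroke and significant ventricular arrhythmia, which the plan itself counts as cardiac events. In Aim 3 these two would probably lower QALYs while adding no cost of their own, to the advantage of whichever strategy has more of them.

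The conclusion rests on two assumptions: that the cardiac events in the QALY weighting are those listed under Study Endpoints, and that the unavailable attachments add no further cost lines. The established extent is 2 of 5 events. No ICER effect is established, in size or direction. For LVAD and CRT the finding is only that collected procedures are not clearly costed. The issue is confined to Aim 3 and is worth correcting before that analysis.

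**What to change.** - Add two lines to d) Costs: stroke hospitalization and ventricular-arrhythmia hospitalization. Take the events from the A4 dates, including the ICD-shock admission field for the second, and price them on the same averaged basis, inflated to the year of analysis, as the rest of the section.
- State in d) Costs and e) Effectiveness a single list of events that enter both the costs and the utility weights.
- Cost LVAD and CRT as collected procedures where ICD and pacemaker implantation does not already cover them, and say which CRT records are treated as covered.
- If the attachments already price any of these items, say so in d) Costs.

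The cost is a few more unit prices applied to dates already collected. One complication is that the A4 field for VT/VF or ICD therapy records an event and not necessarily an admission. Some records may need a stated assumption about whether the patient was hospitalized, ideally with a sensitivity analysis under the opposite assumption.
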